9.1.4 Exploratory analysis of the primary outcome variable

The linear mixed effects model from the primary analysis will also be fitted to the predose and postdose CZP plasma concentrations separately. Adjusted means and 95% CI for each model will be included in the forest plot.

CZP plasma concentrations will additionally be analyzed adjusting for CRP, albumin and BMI. These analyses will be conducted using the same linear mixed effects model used for the primary analysis with CRP, albumin and BMI as a covariate in 3 separate models. Results from these models should be interpreted with caution, due to the small sample size and relatively large number of covariates. Summary tables showing the mean differences and 95% CIs of each trimester vs post-partum estimated from the model contrasts will be presented.

9.2 Immunogenicity

All immunogenicity analyses will be performed using the SS.

9.2.1 Anti-drug antibodies sample status category definitions

Anti-drug antibodies (ADA) will be measured using a three-tiered assay approach: screening, confirmatory and titration assay.

Samples will first be evaluated in the screening assay (reported as ‘negative screen’ or ‘positive screen’), followed by analysis of screened positive samples in the confirmatory assay to confirm the true positivity of the samples (reported as ‘negative immuno-depletion’ or ‘positive immuno-depletion’). Samples that are confirmed as positive in the confirmatory assay will be evaluated in a titration assay to quantify the ADA level and will be reported as titer (reciprocal dilution factor including minimum required dilution [MRD]).

The ADA sample status will be determined for each visit where samples were collected for ADA analysis (both scheduled and any unscheduled visits).

- Sample values that are either ‘negative screen’ or the combination of ‘positive screen’ and ‘negative immuno-depletion’ will be defined as **ADA negative** if corresponding CZP concentrations are equal or below the validated drug tolerance limit of the ADA assay (100 ug/mL CZP) allowing detection of 100ng/mL ADA.

- Sample values that are either ‘negative screen’ or the combination of ‘positive screen’ and ‘negative immunodepletion’ but with corresponding CZP concentrations above the validated drug tolerance limit of the ADA assay will be defined as **ADA inconclusive**.
- Sample values that are ‘positive screen’ and ‘positive immunodepletion’ will be defined as **ADA positive**.
- Samples that could not be tested for ADA status due to inadequate sample volume, mishandling, or errors in sample collection, processing, storage, etc., will be defined as **Missing**.

9.2.2 Anti-drug antibodies participant titer classification

Once determined positive, a study participant’s highest titer will be used to categorize (“titer classification”) the study participant as follows:

- Positive ≤ 32
- Positive $>32 - \leq 128$
- Positive $>128 - \leq 512$
- Positive $>512 - \leq 1024$
- Positive $>1024 - \leq 4096$
- Positive >4096

9.2.3 ADA titer and classification summaries and analyses

The fold difference increase from postpartum value, i.e., the minimum significant ratio (MSR) determined during assay validation, will be reported in the relevant tables, listings and figures. It reflects the fold difference in titer level that is considered higher than the assay variation in titer determination.

The following summaries, figures and listings will be produced using the MSR and will be presented using the SS:

- Summary table displaying the number and percentage of study participants with a positive ADA, negative ADA, inconclusive or missing ADA sample status at the time of each visit by dosing regimen.
- Spaghetti plots of the individual time course plots of ADA titer (y-axis) by time (x-axis) for participants with at least one ADA positive sample status, with one line representing one study participant. Separate plots will be presented for each dosing regimen. Plots may be presented using a semi-logarithmic scale for the ADA titers (ADA negative samples will therefore be excluded from the plot). Time will be presented using gestational week.
- Summary statistics of ADA titers (mean, min, max, geomean) per time point and dosing regimen.
- Summary of titer classification for all study participants who test positive at any visit will be presented by category.
- The ADA results will be listed including the results from the screening assay, confirmatory assay, and titration assay (titer level), the ADA sample status, the drug concentration with indication if the drug level exceeds the ADA assay tolerance for detecting 100 ng/ml ADA or alternative level as defined above (Y/N).

In addition, the following figures will be produced to illustrate the impact of ADA on PK:

- Spaghetti plots of the individual CZP plasma concentrations (each participant corresponding to a line) over time will be produced on a linear and semi-logarithmic scale according to ADA titer classification. Gestational week should be indicated below the x-axis.
- Time course plots of individual CZP plasma concentrations (one plot per participant) superimposed with the participant's corresponding ADA titer over the course of the study will be presented. Plots may be presented using a semi-logarithmic scale for the ADA titers (ADA negative samples will therefore be excluded from the plot). Time will be presented using gestational week.

10 ANALYSIS OF OTHER OUTCOME VARIABLES

10.1 Other outcome variables

The other outcome variables to be presented are:

- CRP levels
- Albumin levels
- BMI

All three parameters will be listed on the SS only and will be used for the exploratory CZP model.

11 SAFETY ANALYSES

All safety analyses will be performed using the SS.

11.1 Pregnancy outcome

Pregnancy outcome by study participant will be included in a listing.

11.2 Infant illnesses

Illnesses reported for each infant by study participant will be included in a listing.

11.3 Adverse events

All AEs will be coded using the Medical Dictionary for Regulatory Activities (MedDRA v24.1 or later version) and characterized as treatment emergent.

The occurrence and incidence of TEAEs will be summarized by MedDRA system organ class and preferred term. The TEAEs will also be summarized by intensity and by relationship to CZP. TEAEs leading to discontinuation and serious TEAEs will also be summarized.

The following TEAE tables will be produced:

- Incidence of TEAEs Overview
- Incidence of TEAEs by SOC, HLT and PT
- Serious TEAEs
- Non-serious TEAEs
- TEAEs leading to death

- TEAEs leading to hospitalization or death
- TEAEs leading to study discontinuation
- Incidence of TEAEs by Maximum Severity
- Incidence of TEAEs by Maximum relationship
- Incidence of TEAEs by Trimester

The following TEAE of interest will be summarized in stand-alone tables:

- Serious infections including opportunistic infections (see Section 11.3.1)
- Malignancies or unspecified tumours including lymphoma
- Malignant Tumours
- Demyelinating-like disorders
- Aplastic anemia, pancytopenia, thrombocytopenia, neutropenia, and leucopenia
- Serious bleeding events

For the following AEs of interest, no additional tables will be provided, as these are included in the standard AE summaries:

- Congestive heart failure
- Lupus and lupus-like syndrome
- Serious skin reactions (e.g., Stevens Johnson Syndrome, toxic epidermal necrosis, and erythema multiforme).

Separate tables will be created to summarize each of the above TEAEs of interest by system organ class, high level term, and PT, where the TEAEs of interest are identified using standardized MedDRA queries (SMQ). An additional review cycle to confirm the targeted events will be implemented for opportunistic infections as described in Section 11.3.1.

All TEAEs and serious TEAEs will be listed using the SS. Details of serious TEAEs, TEAEs leading to death or study discontinuation will be listed. For results disclosure on public registries (e.g., ClinicalTrials.gov), TEAEs and serious TEAEs will be published.

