5.1 Inclusion criteria

To be eligible to participate/enroll in this study, all of the following criteria must be met at the Screening Visit (Visit 1). Eligibility must also be confirmed at Enrollment Visit (Visit 2), ie, just prior to blood sampling for PK. If a participant does not initially meet the enrollment criteria, she may be rescreened; however, a study participant may not be enrolled for consecutive pregnancies.

Participants are eligible to be included in the study only if all of the following criteria apply:

Age

1. Participant must be ≥ 18 years of age at the time of signing the ICF.

Type of participant and disease characteristics

2. Participant must be considered reliable and capable of adhering to the protocol and visit schedule according to the judgment of the investigator.
3. Participant is pregnant and ≤ 10 weeks gestation at the time of enrollment.
4. Participant must have been on stable, maintenance dose CZP treatment for at least 12 weeks independent of and prior to being enrolled in this study, for an approved indication in accordance with her treating physician.
5. Participant expects to continue CZP therapy throughout pregnancy and for at least 12 weeks postpartum.
6. Participant has a negative interferon gamma release assay (IGRA) or tuberculin skin test (TST) within the prior 6 months, and there has been no change in the study participant's clinical status, or social, family, or travel history. Participants with documented Bacillus Calmette–Guérin (BCG) vaccine and at low risk for TB may enroll without having a TB test performed.

Sex

7. Participants who are female.

Informed consent

8. Participant is capable of giving signed informed consent as described in Section 10.1 (Appendix 1) which includes compliance with the requirements and restrictions listed in the ICF and in this protocol.

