9.3.3 Safety analyses

All safety analyses will be performed using the SS. All safety variables will be summarized by study part (each sampling point or postpartum).

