3 DATA ANALYSIS CONSIDERATIONS

3.1 General presentation of summaries and analyses

Statistical analysis and generation of tables, figures, study participant data listings, and statistical output will be performed using SAS® Version 9.3 or higher. All tables and listings will use Courier New font size 9.

Descriptive statistics will be displayed to provide an overview of the study results.

For categorical parameters, the number and percentage of study participants in each category will be presented. Unless otherwise noted, the denominator for percentages will be based on the number of study participants included in the respective analysis set. Study participants with missing PK/ADA data will be addressed in [Section 4.2.3](#). Other missing data can generally be accounted for using one of the following approaches:

- Percentages will be summarized based on all study participants in the analysis set and a “Missing” category (corresponding to study participants with missing data for the variable being summarized) will be included as the last row in the list of categories being summarized.
- Percentages will be based only on those study participants with observed data for the variable being summarized. As the denominator may be different from the number of study participants in the analysis set being considered, the denominator should be displayed in the table. The general format for displaying this will be “n/Nsub (%)”, where n=number participants in a category and Nsub=total number of participants with observed data.

The approach to be considered will be further specified in the relevant section of the variable of interest.

Unless otherwise noted, all percentages will be displayed to one decimal place. No percentage will be displayed for zero counts, and no decimal place will be presented when the percentage is 100%.

Unless stated otherwise, continuous endpoints will be summarized by timepoints.

For continuous parameters, descriptive statistics will include number of study participants with available measurements (n), arithmetic mean, standard deviation (SD), median, minimum, and maximum (unless otherwise stated). If n=3, only n, mean, median, minimum and maximum will be displayed. If n<3, only n, minimum and maximum will be displayed. For both cases, any summary statistics that are not displayed will be replaced with ‘NA’ and explained in a footnote.

Decimal places for descriptive statistics will always apply the following rules:

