3.2.2 Study periods

The study consists of a Screening Period, Sampling Period (consisting of a Pregnancy Period and Postpartum Period), and a Safety Follow-up (SFU) contact, as described below. Gestational week (i.e., week of gestational age) is determined from the time since the first day of the last menstrual period or, if the participant had undergone in vitro fertilization (IVF), from the date of birth and gestational age recorded for the pregnancy outcome and then back-calculated to get the gestational week for each PK sample.

- Screening Period: Starts at the confirmation of pregnancy at screening and ends at the start of the enrolment date (Participant having taken CZP for at least 12 weeks at the same dosing regimen prior to the Enrollment Visit, which must take place at ≤ 10 weeks gestational age).
- Sampling Period: The total study duration for a study participant will be a maximum of 53 weeks (40 weeks gestation period and up to 13 weeks (± 3 days) postpartum).
 - Pregnancy Period: Starts at enrolment and ends on the day of delivery. Pregnancy may take the entire length of the gestation period (up to 40 weeks).
 - Postpartum Period: Starts the day after the date of delivery and ends after the final postpartum sample is taken.
 - Trimesters: Defined using the gestational week and distinguished as first (up to 12 weeks and 6 days’ gestation), second (13–28 weeks and 6 days’ gestation), and third (any time at or after 29 weeks’ gestation)
- Safety Follow-up contact: The SFU visit will be defined for all study participants who complete the study, or for study participants who discontinue early including those who discontinue from CZP. For participants who complete the study, the SFU will be conducted 5 weeks (± 5 days) after final study visit. For participants who discontinue, the SFU visit will still be completed.

In case that the SFU date is not available, the last contact date will be used as end of the SFU period. A participant is considered to have completed the study if she has completed all phases of the study per protocol including the final study contact (SFU).

The end of the study is defined as the date of the SFU/last contact of the last participant in the study.

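### The adverse-event table by trimester has no denominator or exposure rule of its own, so unequal observation time and attrition can print as trimester differences.

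*SAP*

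**What the plan says.** - SAP 11.3 lists "Incidence of TEAEs by Trimester" among the adverse-event tables. It gives no denominator, no exposure adjustment and no caveat for it.
- SAP 3.1 sets a default for percentages that holds wherever nothing else is specified: "the denominator for percentages will be based on the number of study participants included in the respective analysis set". SAP 11 places all safety analyses on the Safety Set, and SAP 3.5.3 fixes membership by dosing status at Screening.
- SAP 3.2.2 defines the trimesters by gestational week: "first (up to 12 weeks and 6 days’ gestation), second (13–28 weeks and 6 days’ gestation"), then "third (any time at or after 29 weeks’ gestation"). On the length of pregnancy it says: "Pregnancy may take the entire length of the gestation period (up to 40 weeks").
- Enrolment is limited by Protocol 5.1: "Participant is pregnant and ≤ 10 weeks gestation at the time of enrollment". Adverse events are collected from signature of the consent form (Protocol Table 1-1 and 8.3.1), and consent comes after pregnancy is confirmed (Protocol 1.1, SAP 2.3).
- Protocol 7.2 ends participation after a spontaneous abortion.
- On the layout of safety summaries, Protocol 9.3.3 says: "All safety variables will be summarized by study part (each sampling point or postpartum").

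**The concern.** Safety across the course of pregnancy is a secondary objective, and this is the only adverse-event table in SAP 11.3 that splits events by period. Readers will set its columns side by side. Two features can make those columns differ when the event rate does not.

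First, each woman's trimester 1 is cut off on the left, because nothing is recorded before consent, while trimester 2 is seen in full by anyone who stays in the study. A crude percentage rises with the length of the window. Second, a woman who has left still counts in the denominator of later trimesters although she can no longer contribute an event there. The likely result is a low figure in trimester 1, a high one in trimester 2 and a somewhat lowered one in trimester 3, which could be taken for a pattern of risk over pregnancy.

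**Working it through.** The plan states no figure for this table and derives its sample size from no formula, so there is nothing to reproduce. The stated maximum duration does agree with its parts: 40 + 13 = 53 weeks.

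**1. Observation windows** (limits from SAP 3.2.2; the consent week is an assumption)

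- Trimester 1: 13 minus the consent week. Week 6 gives 7 weeks, week 8 gives 5 and week 10 gives 3. Consent at week 4 would give 9.
- Trimester 2: 29 − 13 = 16 weeks.
- Trimester 3, read as ending at delivery: 40 − 29 = 11 weeks, or 37 − 29 = 8 for delivery at 37 weeks.
- Ratio of trimester 2 to trimester 1 time: 16/7 = 2.3 to 16/3 = 5.3 for consent at weeks 6 to 10. At week 4 it is 16/9 = 1.8.

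**2. Crude incidence with no true trimester effect**

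With a constant rate λ per woman-week and no dropout, the chance of at least one event in a window of t weeks is 1 − exp(−λt). The documents give no λ, so a range of 0.01 to 0.10 is assumed.

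| λ | Consent week | Trimester 1 | Trimester 2 | Trimester 3 | T2/T1 |
|---|---|---|---|---|---|
| 0.01 | 6 | 6.8% | 14.8% | 10.4% | 2.19 |
| 0.01 | 10 | 3.0% | 14.8% | 10.4% | 5.00 |
| 0.02 | 6 | 13.1% | 27.4% | 19.7% | 2.10 |
| 0.02 | 10 | 5.8% | 27.4% | 19.7% | 4.70 |
| 0.05 | 6 | 29.5% | 55.1% | 42.3% | 1.86 |
| 0.05 | 10 | 13.9% | 55.1% | 42.3% | 3.95 |
| 0.10 | 6 | 50.3% | 79.8% | 66.7% | 1.59 |
| 0.10 | 10 | 25.9% | 79.8% | 66.7% | 3.08 |

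The ratio runs from about 1.6 to 5.0 over this grid.

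**3. Denominator**

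Printed percentage = percentage among women observed × (women observed ÷ Safety Set). In a set of 20, each woman absent from a trimester lowers its printed figure by a factor of 1/20, or 5% in relative terms. The documents do not say how many women are expected to be under observation in trimesters 2 and 3, so the total effect cannot be computed.

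**4. What person-time does**

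Take 20 women, consent at week 10, no dropout and λ = 0.05. Person-weeks are 20 × 3 = 60, 20 × 16 = 320 and 20 × 11 = 220. Expected events are 3, 16 and 11. The rate is 3/60 = 16/320 = 11/220 = 5.0 per 100 person-weeks in every trimester. Correcting the denominator alone would not achieve this: with everyone retained, the percentages stay at 13.9%, 55.1% and 42.3%.

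**The case against.** The table is descriptive, the study is small and exploratory, no test between trimesters is planned, and all events are also listed. That is right, and it limits the harm to misreading.

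Several stronger statements that a reader might infer do not stand:

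- *That the SAP expressly divides every trimester by the Safety Set.* SAP 11.3 says nothing on this. It follows from the SAP 3.1 default because nothing overrides it, and no table shell is among the documents.
- *That 15 of 20 women will still be observed in trimester 3.* The ratio of enrolled to evaluable participants in Protocol 9.8 and SAP 2.4 concerns PK data. A woman can lack PK samples, or interrupt dosing, and still be followed for adverse events.
- *That trimester 1 observation starts at enrolment.* It starts at consent, which comes earlier, so the 3 to 7 weeks hold only if weeks 6 to 10 are read as consent weeks. The window is longer if consent is earlier.
- *That postpartum is plainly left out.* SAP 3.2.2 names three trimesters, but SAP 4.1 and 9.1.2 treat postpartum as a fourth level of the trimester variable. The label is ambiguous. What is clear is that SAP 11.3 does not say, while Protocol 9.3.3 names a postpartum part.

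There is also a bias the other way: SAP 4.2.1 sets completely unknown onset dates to enrolment, which falls in trimester 1. It has no reason to cancel the window effect, and it should be disclosed.

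**Conclusion.** The point holds. Window lengths follow from the SAP's own trimester limits and the start of collection at consent, and the denominator follows from its default rule. Under a constant rate, crude incidence in trimester 2 would appear about 1.6 to 5.0 times that in trimester 1, given assumed rates of 0.01 to 0.10 per woman-week and assumed consent at weeks 6 to 10. The direction does not depend on the rate chosen; the size does. Women who leave early, for instance after a spontaneous abortion, would lower later percentages further by an unknown amount. No inference in the plan is invalidated. What is at risk is a fair reading of one descriptive table that carries the period view of a secondary objective.

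**What to change.** In SAP 11.3, define the table with columns for trimesters 1, 2, 3 and postpartum, and show for each:

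- the number of women under observation in the period, used as the denominator for n (%);
- person-weeks. For the trimesters, count from the later of consent or trimester start to the earliest of trimester end, delivery or last contact. For postpartum, count from the day after delivery to last contact, since adverse events are collected up to the Safety Follow-up;
- events per 100 person-weeks.

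If an interval is given, base it on women with a first event in the period over time to that event, or use a method that allows for repeated events within a woman. An exact Poisson interval on all events would be too narrow if events cluster within women. State where events after a pregnancy loss are counted. Add a footnote that trimester 1 is observed only from consent, and that completely unknown onset dates are set to enrolment and so add events to trimester 1.

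The cost is SAP wording and one reprogrammed table. The plan already relies on event onset, delivery and last-contact dates, and consent is documented for every participant. With about 20 women the rates will be imprecise, which the table should make visible.

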11.3.1 Identification of opportunistic infections

A summary of opportunistic infections (including tuberculosis) will include all TEAEs identified using UCB-defined search criteria.

Identification Process

The steps below outline 2 ways (both programmatically and after manual review) in which opportunistic infections (or potential opportunistic infections) can be identified using standardized MedDRA queries (SMQ):

Step 1 [programmatic identification]: All TEAEs from 'Opportunistic infections (SMQ)' with a narrow scope are considered as automatically identified opportunistic infection, regardless of seriousness.

Step 2 [manual identification]: All other TEAE in the ‘Opportunistic infections (SMQ)’ with a broad scope will be evaluated on a case-by-case basis by the study physician to determine whether it is a true opportunistic infection (OI) of interest or not.

Review Process

A final listing for opportunistic infections (in the format described below) will be produced and reviewed by the study physician prior to finalizing the database.

The study programming team will produce an Excel listing of all AEs from the ADaM domain for participants with at least 1 TEAE falling within the broad scope of the ‘Opportunistic infections (SMQ)’ allowing a review of all the participants’ AEs to establish OI of interest. The Excel listing will contain the following columns (using the descriptions below as the column headings in the Excel listing):

- Study ID
- Unique Participant ID
- AE Term (Verbatim)
- AE Preferred Term
- AE System Organ Class
- AE High Level Term
- AE Low Level Term
- Date of Onset
- Outcome of Adverse Event
- Date of Outcome
- TEAE Flag
- Serious Adverse Event?
- Relationship to Study Medication
- Intensity
- Action Taken with IMP
- Opportunistic Infection – Automatic; code and scope (Y/N)
- Opportunistic Infection – Manual Review; code and scope (Y/N)
- Flag for previously reviewed? (NEW/OLD)
- Data Cut Date
- Opportunistic Infection – Final Adjudication (Y/N)

Note the following about the final 5 variables in this listing:

- *Opportunistic Infection – Automatic:* This is flagged as “Y” if the criteria for automatic selection as described in “Step 1” of the identification process are met.

- *Opportunistic Infection – Manual Review*: This is flagged as “Y” if the criteria for case-by-case selection as described in “Step 2” of the identification process are met.
- *Flag* – This has a value of either “NEW” or “OLD”. It is marked as “NEW” if the event is appearing for the first time in that run of the listing. Otherwise, if it has appeared previously, it is marked as “OLD”. Unique records are determined by USUBJID AESPID for purposes of identifying whether an event has been modified from a previous run.
- *Date* – Only for cases where Flag is “NEW”, this field will be populated with the data cut date for that particular run of the listing.
- *Opportunistic Infection – Final Adjudication* – For new events, this is always left blank by the programmers. It will be completed by the study physician for every event that appears in the listing. For events adjudicated as opportunistic, the field will be populated with a “Y”.

Following the review by the study physician, the *Opportunistic Infection – Final Adjudication* column will be completed (as described above), and the spreadsheet will be returned to the study programming team via e-mail. The decisions documented in the returned file will be merged with AE data for final reporting in a summary table and flagged in the All Adverse Events listing.

